## 4. ANALYSIS POPULATIONS

### 4.1 Analysis Populations

#### **Safety Population**

The safety population will include all patients who received at least one dose of study drug (active or placebo).

#### **Pharmacokinetic Population**

Samples from all patients receiving the active drug will be assayed even if the patients do not complete the study. All patients receiving the active drug who comply sufficiently with the protocol and display an evaluable PK profile (e.g., exposure to treatment, availability of measurements and absence of major protocol violations) will be included in the statistical analyses.

#### **Pharmacodynamic Population**

All patients who received the study drug (active or placebo) and had at least one postdose measurement of any of the PD assessment will be included in the statistical analyses.

### 4.2 Preliminary Data and Interim Analysis

Celerion has not been contracted to complete any interim safety, PK, and PD analyses.

## 5. TREATMENT DESCRIPTIONS

Patients will receive a single infusion dose of 0.25 mg/kg xisomab 3G3, 0.5 mg/kg xisomab 3G3, or matching placebo on Day 1 at Hour 0. The dose will be administered proximal to the dialyzer cartridge, into the arterial line immediately after start of HD.

Planned doses for each cohort of the study are as follows:

Cohort 1: 0.25 mg/kg xisomab 3G3 or matching placebo

Cohort 2: 0.5 mg/kg xisomab 3G3 or matching placebo

The patients' weight recorded at check-in will be used to calculate the study drug dose.

Treatments will be described as follows:

Cohort	Treatment	Short Description (used in text)	Long Description (used in Tables Figures and Listings)
Cohorts 1 & 2	P	Placebo (Pooled)	Single IV Infusion of Placebo (Pooled)
Cohort 1	A	0.25 mg/kg xisomab 3G3	Single IV Infusion of 0.25 mg/kg xisomab 3G3
Cohort 2	B	0.5 mg/kg xisomab 3G3	Single IV Infusion of 0.5 mg/kg xisomab 3G3

## **6. PHARMACOKINETIC ANALYSIS**

### **6.1 Measurements and Collection Schedule**

For all patients, blood samples for the determination of free xisomab 3G3 will be collected at predose (hour 0, at least 1 hour prior the start of HD session) and at 0.167, 0.5, 1, 2, 3, 4, 6, 8, 12, 16, 24, 48, 96, 120, 144, and 192 hours after xisomab 3G3 start of infusion.

All concentration data will be included in the calculation of the individual PK parameters, the individual concentration-time plots (based on actual sample times), and in the mean concentration-time plots (based on nominal sample times). However, if there are any significant deviations from nominal sample times, some concentration data may be excluded from mean concentration-time plots and/or additional concentration-time plots of the mean data may be provided. All deviations and excluded data will be provided and discussed in the CSR.

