6 STUDY EVENTS FLOW CHART

| Study Procedures ^{a:} | Screening ^{b:} (Day -37 to Day -9) | Study Days | | | | | |
|--|---|-------------------|------------------|------------------|------------------|------------------|------------------|
| | | Evaluation Period | | | | | |
| | | -8 | -7 | -6 | -5 | -4 | -3 |
| | | HD ^{d:} | HD ^{d:} | HD ^{d:} | HD ^{d:} | HD ^{d:} | HD ^{d:} |
| Days → | C-I ^{e:} | start | end | start | end | start | end |
| HD → | | | | | | | |
| Hours → | | | | | | | |
| Administrative Procedures | | | | | | | |
| Informed Consent | X | | | | | | |
| Inclusion/Exclusion Criteria | X | X | | | | | |
| Medical History | X | | | | | | |
| Safety Evaluations | | | | | | | |
| Full Physical Examination ^{e:} | X | X | | | | | |
| Height | X | | | | | | |
| Weight | X | X | X ^{f:} | X ^{g:} | X | X ^{g:} | X |
| 12-Lead Safety ECG | X | X | | | | | |
| Vital Signs (HR, BP, RR, and T) | X | X | X ^{f:} | | X ^{f:} | | X ^{f:} |
| Bleeding of Access Site | | | | X ^{g:} | | X ^{g:} | |
| Hem, Serum Chem ^{h:} , and UA ^{i:} | X | X | | | | | X ^{g:} |
| Coagulation ^{j:} | X | | X ^{f:} | X ^{g:} | X ^{f:} | X ^{g:} | X ^{f:} |
| Platelet Count ^{s:} | | | X ^{f:} | X ^{g:} | X ^{f:} | X ^{g:} | X ^{f:} |
| Serum Pregnancy Test (♀ only) | X | X | | | | | |
| Serum FSH (PMP ♀ only) | X | | | | | | |
| Urine/Saliva Drug and Alcohol Screen | X | X | | | | | |
| HIV/Hepatitis Screen | X | | | | | | |
| AE Monitoring | | | | | X | | |
| ConMeds Monitoring | X | | | | X | | |
| Other Procedures | | | | | | | |
| Blood BUN and Potassium (for Kt/V and URR) ^{s:} | | | X ^{f:} | X ^{g:} | X ^{f:} | X ^{g:} | X ^{f:} |
| Dialysate Analysis | | | X ^{k:} | X ^{k:} | X ^{k:} | X ^{k:} | |
| Visual Assessment and Processing of Dialyzer Membrane | | | | X ^{l:} | | X ^{l:} | X ^{l:} |
| Confinement in the CRU | | | | | X | | |
| Visit | X | | | | | | |

| Study Procedures ^{a:} | Study Days | | | | | | | | | | | | | | | | | | | |
|--|-----------------|-------|-----------------|---|---|-----------------|---|---|---|----|----|----|-----------------|-----------------|-----------------|-----------------|-----------------|-----------------|-----------------|-----------------|
| | PK/PD Period | | | | | | | | | | | | | | | | | | | |
| | Days → | 1 | | | | | | | | | | 2 | 3 | | | 4 | 5 | | 6 | |
| Hours → | 0-0.016 | 0.167 | 0.5 | 1 | 2 | 3 | 4 | 6 | 8 | 12 | 16 | 24 | 48 | start | end | 72 | 96 | start | end | 120 |

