| | Hours → | | start | end | start | end | start |
| Safety Evaluations | | | | | | | |
| Abbreviated Physical Examination ^{e:} | | | | | | | X ^{r:} |
| Weight | | X ^{f:} | X ^{g:} | X ^{f:} | X ^{g:} | X ^{f:} | X ^{g:} |
| 12-Lead Safety ECG | | | | | | | X ^{r:} |
| Vital Signs (HR, BP, RR, and T) | | X ^{f:} | | X ^{f:} | | X ^{f:} | X ^{r:} |
| Bleeding of Access Site | | | | | | | X ^{g:} |
| Hem, Serum Chem ^{h:} , and UA ^{i:} | | | | | | | X ^{r:} |
| Coagulation ^{j:} | | | | | | X ^{f:} | X ^{g:} |
| Platelet Count ^{s:} | | | | | | X ^{f:} | X ^{g:} |
| Serum Pregnancy Test (♀ only) | | | | | | | X ^{r:} |
| AE Monitoring | | | | X | | | X |
| ConMeds Monitoring | | | | X | | | |
| Study Drug Administration / PK/PD/Immunogenicity | | | | | | | |
| Blood for free xisomab 3G3 PK | | | | | | | X ^{r:} |
| Blood for free xisomab 3G3 PD (aPTT) ^{s:} | | X ^{o:} | | X ^{o:} | | | |
| Blood for Immunogenicity | | | | | | | X ^{r:} |
| Other Procedures | | | | | | | |
| Blood BUN and Potassium (for Kt/V and URR) | | | | | | X ^{f:} | X ^{g:} |
| Dialysate Analysis | | | | | | X ^{k:} | X ^{k:} |
| Visual Assessment and Processing of Dialyzer Membrane | | | | | | | X ^{l:} |
| Return Visits | | | X | | X | | X |

- a: For details on Procedures, refer to [Section 13](#)
- b: Within 28 days prior to Day -8.
- c: Patients will be admitted to the CRU on Day -8, at the time indicated by the CRU and will remain confined up to Day 6 or prior early termination.
- d: Patients will undergo hemodialysis 3 times a week, on Day -7, Day -5, Day -3, and Day 1, Day 3, Day 5, Day 8, Day 10, and Day 12. For each patient, the hemodialysis will last at least 3 hours as per patient standard schedule which will be the same throughout the study.
- e: Symptom-driven physical examination may be performed at other times, at the PI's or designee's discretion.
- f: To be performed ~ 1 hour prior to the start of hemodialysis.
- g: To be performed at the end of hemodialysis.
- h: Samples for serum chemistry will be obtained following a fast of at least 4 hours, however, in case of dropouts or rechecks, patients may not have fasted for 4 hours prior to the serum chemistry sample is taken.
- i: For anuric patients, urinalysis may not be performed.
- j: Coagulation parameters (activated partial thromboplastin time [aPTT], prothrombin time [PT], and international normalized ratio [INR]).

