13.8 Blood Volume Drawn for Study Assessments

Table 4: Blood Volume during the Study

| Sample Type | Number of Time Points | Approximate Volume per Time Point * (mL) | Approximate Sample Volume Over Course of Study (mL) |
|---|-----------------------|--|---|
| Screening laboratory safety tests (including hematology, serum chemistry, serology, and coagulation), FSH (for postmenopausal female patients only) and serum pregnancy (for female patients only). | 1 | 16 | 16 |
| On-study hematology and serum chemistry(this includes serum pregnancy for female patients only when scheduled at the same time) | 4 | 12.5 | 60 |
| On-study coagulation (PT/INR and aPTT) | 16 | 3.5 | 56 |
| On-study platelet count only ** | Up to 14 | 3.5 | Up to 49 |
| On-study BUN and potassium only ** | Up to 14 | 3.5 | Up to 49 |
| Blood for PD (aPTT only) ** | Up to 17 | 2.7 | Up to 45.9 |
| Blood for PK (free xisomab 3G3) | 16 | 10 | 160 |
| Blood for Immunogenicity | 2 | *** | *** |
| Total Blood Volume (mL)→ | | | Up to 435.9 † |

- * Represents the largest collection tube that may be used for this (a smaller tube may be used).
- ** Platelet count, BUN and potassium, and aPTT value will be taken from the hematology, serum chemistry, and coagulation sample, respectively, when these are scheduled to be collected at the same time. Samples will not be taken twice at a same timepoint
- *** Sample for immunogenicity will be taken from the PK sample tube. If this sample does not correspond with a PK sample, an extra 10 mL of blood sample will be collected.
- † If additional safety, PK, or PD analysis is necessary or if larger collection tubes are required to obtain sufficient plasma/serum for analysis, additional blood may be obtained (up to a maximum of 50 mL; this volume could be exceeded only with agreement of the PI on a case-by-case basis).

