## 7.2 Data Summarization and Presentation of PD Parameters

### 7.2.1 aPTT

**Sample Collection:** Samples for the coagulation parameter (aPTT) will be collected at screening, pre- and post-dialysis on Days -7, -5, -3, 1, 3, 5, and 12. Additional samples for aPTT will be collected following xisomab 3G3/placebo dosing on Day 1 at predose (hour 0, at least 1 hour prior the start of HD session) and at 0.167, 0.5, 1, 2, 3, 4, 6, 8, 12, 16, 24, 48, 96, 120, 144, and 192, hours after xisomab 3G3 start of infusion.

**Baseline Calculation Method Following Day 1 Dosing:** Following xisomab 3G3 dosing on Day 1, aPTT change from baseline will be calculated by dividing postdose aPTT values from average of pre-dose baseline (the average of pre-dialysis aPTT values on Days -7, -5, -3, and 1 will be calculated as pre-dose baseline).

**Fold change in aPTT values:** The fold change in aPTT values on Days -7, -5, -3, 1 (only pre- and post-dialysis aPTT values on Day 1), 3, 5, and 12 will be calculated by dividing the post-dialysis aPTT/pre-dialysis aPTT values for each day separately.

aPTT values will be extracted from the clinical laboratory database and descriptive statistics will be generated using SAS® version 9.3 or higher. Following Day 1 xisomab 3G3 dosing, a table will be presented for the aPTT change from baseline with descriptive statistics.

aPTT values will be listed and summarized by treatment and time points in Tables and Figures for all subjects in the Safety Population (2 active dose levels and pooled placebo). aPTT values will be presented with the same level of precision as received from the clinical laboratory database. Summary statistics, including n, Mean, SD, CV%, SEM, minimum, median, and maximum will be calculated for all nominal values time points. Excluded subjects will be included in the aPPT values tables, but will be excluded from the summary statistics and noted as such in the tables.

Mean and individual aPTT values-time and change from baseline-time profiles will be presented on linear scale. Linear mean plots will be presented with and without SD.

The level of precision for the aPPT values summary statistic will be presented as follows:

- minimum/maximum: in same precision as in the clinical laboratory database
- Mean/median: in one more level of precision than minimum/maximum
- SD/SEM: in one more level of precision than Mean/median
- n will be presented as an integer
- CV% will be presented to the nearest tenth

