**Notes for Generating the Actual Table:**

- Please use CPConcl template
- Per study design needs, the following changes are made to this table relative to Celerion standard: columns <Treatment Sequence> and <Study Period> will be removed.
- Concentrations will be presented to the same precision as in the bio data.
- aPTT values will be presented to the same precision as in the clinical laboratory data.
- Summary statistics presentation with respect to the precision of the bio data or clinical laboratory data: n = integer; Mean and Median +1; SD and SEM +2, Minimum and Maximum +0, CV% to 1 decimal
- PK Time points are: predose (hour 0) and 0.167, 0.5, 1, 2, 3, 4, 6, 8, 12, 16, 24, 48, 96, 120, 144, and 192 hours postdose (additional time points might be added depending on the conduct of the study)
- For Tables 14.2.5.1.1 through 14.2.5.1.3, aPTT values will be reported during the course of the study from Days -7 through 12 with adding "Day" above the "Sampling Time".
- For Tables 14.2.5.1.3 and 14.2.5.1.6, there will be no summary statistics

Program: /CAXXXX/sas\_prg/pksas/pk-conc-tables.sas DDMMYYYY HH:MM  
Program: /CAXXXX/sas\_prg/pksas/pk-conc-tables-sig.sas DDMMYYYY HH:MM  
Program: /CAXXXX/sas\_prg/pksas/adam\_conc.sas DDMMYYYY HH:MM

Tables 14.2.1.1.4 and 14.2.1.1.5 will be in the following format:

Table 14.2.1.1.4 Plasma Xisomab 3G3 Pharmacokinetic Parameters Following a Single IV Infusion of 0.25 mg/kg Xisomab 3G3 (Pharmacokinetic Population)

Subject Number	Parameters					
	param1 (units)	param2 (units)	param3 (units)	param4 (units)	param5 (units)	param6 (units)
X	XXX	X.XX	XXX	XXX	XX.X	X.XXX
X	XX.X	X.XX	XXX	XXX	XX.X	X.XXX
X	XXX	X.XX	XXX	XXX	XX.X	X.XXX
X	XX.X	X.XX	XXX	XXX	XX.X	X.XXX
X	XX.X	X.XX	XXX	XXX	XX.X	X.XXX
X	X.XX	X.XX	XXX	XXX	XX.X	X.XXX
X	XXX	X.XX	XXX	XXX	XX.X	X.XXX
n	XX	XX	XX	XX	XX	XX
Mean	XXX.X	X.XXX	XXX.X	XXX.X	XX.XX	X.XXXX
SD	XX.XX	XX.XX	XX.XX	XX.XX	XX.XX	XX.XX
CV%	XX.X	XX.X	XX.X	XX.X	XX.X	XX.X
SEM	XX.XX	XX.XX	XX.XX	XX.XX	XX.XX	XX.XX
Minimum	XX.X	X.XX	XXX	XXX	XX.X	X.XXX
Median	XX.XX	X.XXX	XXX.X	XXX.X	XX.XX	X.XXXX
Maximum	XXX	X.XX	XXX	XXX	XX.X	X.XXX
Geom Mean	XXX.X	X.XXX	XXX.X	XXX.X	XX.XX	X.XXXX
Geom CV%	XX.X	XX.X	XX.X	XX.X	XX.X	XX.X

. = Value missing or not reportable.

---

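### The SAP gives PK and aPTT one shared sampling list ending at 144 h and 192 h, which match no protocol visit; the late samples the protocol does plan (aPTT on Days 8 and 10, PK on Day 12) have no matching nominal time

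*SAP*

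**What the plan says.** **SAP.** Section 6.1 lists PK samples at predose and 16 postdose times, the last of them "24, 48, 96, 120, 144, and 192 hours after xisomab 3G3 start of infusion". Section 7.2.1 repeats the list for aPTT: it opens with "Additional samples for aPTT will be collected following xisomab 3G3/placebo dosing on Day 1 at predose" and closes with "24, 48, 96, 120, 144, and 192, hours after xisomab 3G3 start of infusion". The shell note in Section 11.3 for the concentration and aPTT tables gives the PK times again, ending "24, 48, 96, 120, 144, and 192 hours postdose". Separately, 7.2.1 schedules aPTT before and after dialysis on Days -7, -5, -3, 1, 3, 5 and 12. Section 9 reports a change in dialysis length and in the related BUN and potassium timing, says nothing about PK or aPTT times, and otherwise describes the SAP as consistent with the protocol.

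**Protocol.** In the Section 6 flow chart, confinement ends on Day 6 and return visits are marked on Days 8, 10 and 12. Footnote d places dialysis "on Day -7, Day -5, Day -3, and Day 1, Day 3, Day 5, Day 8, Day 10, and Day 12". After 120 h the chart shows one PK sample (footnote r, Day 12) and two aPTT samples (footnote o, taken before dialysis, Days 8 and 10). Table 4 in Section 13.8 counts 16 time points in the row beginning "Blood for PK (free xisomab 3G3" and up to 17 in the aPTT-only row.

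**The concern.** The two documents disagree about when late samples exist, and the SAP's times are the ones that would be programmed. PK concentration summaries and aPTT summaries are produced by nominal time, mean PK plots use nominal times, and the mean aPTT figures have hours from start of infusion on the x-axis. A wrong nominal time therefore passes straight into the displays.

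Apart from the Day 12 dialysis samples, Days 8 and 10 are the only scheduled aPTT measurements after discharge. They show how long the anticoagulant effect of a single dose lasts. The SAP states a goal of several days' effect per dose, and the protocol reports that time for aPTT to return to baseline rose with dose in the first-in-human study. For PK, the stake is a table with two columns that no planned sample fills and no listed column for the last planned one.

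**Working it through.** **1. Day-to-hour scale.** The flow chart header for Days 3 to 6 reads "48 | start | end | 72 | 96 | start | end | 120", and footnote p ties the discharge sample to 120 h. Hence hour = (Day - 1) × 24. This gives Day 2 = 24, Day 3 = 48, Day 4 = 72, Day 5 = 96 and Day 6 = 120, all as printed.

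**2. Reproducing Table 4.** The flow chart has predose (1), then 0.167, 0.5, 1, 2, 3, 4, 6, 8, 12, 16 and 24 h (11), then 48, 96 and 120 h (3). That is 1 + 11 + 3 = 15 points common to PK and aPTT.
- PK: 15 + Day 12 = 16. Table 4 says 16.
- aPTT: 15 + Day 8 + Day 10 = 17. Table 4 says up to 17.

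Both counts reproduce, which confirms where the footnotes place the late samples.

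**3. The SAP list.** The same 15 points + 144 h + 192 h = 17, for both PK and aPTT. That equals the protocol's aPTT count and is one more than its PK count.

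**4. Late times side by side.**

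| Day | Hour | Protocol visit | Planned PK | Planned extra aPTT | In SAP list |
|---|---|---|---|---|---|
| 7 | 144 | none | no | no | yes |
| 8 | 168 | return visit | no | yes, before dialysis | no |
| 9 | 192 | none | no | no | yes |
| 10 | 216 | return visit | no | yes, before dialysis | no |
| 12 | 264 | return visit | yes | no (coagulation sample before and after dialysis) | no |

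**5. Size of the label error, if 144 h and 192 h stand for Days 8 and 10.** 144 - 168 = -24 h and 192 - 216 = -24 h, which is 24/168 = 14% and 24/216 = 11% of the true time. For a sample drawn exactly 1 h before a session starting at the same clock time as on Day 1, the error is 23 h. Day 12 lies 264 - 192 = 72 h beyond the last listed time.

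**6. Will late PK be quantifiable?** Assume mono-exponential decline with the first-in-human values at 0.5 mg/kg (Cmax 11,250 ng/mL, half-life 16.638 h; protocol Table 1) and the expected lower limit of 50 ng/mL (SAP 6.2). Time to the limit = 16.638 × log2(11,250/50) = 16.638 × 7.814 = about 130 h. On that assumption a Day 12 value would be below quantitation. Those values come from healthy subjects; the behaviour in ESRD is unknown.

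**The case against.** **The SAP never says which day 144 h or 192 h represents.** A reader might infer that Day 8 and Day 10 aPTT will certainly be shown 24 h early. The documents do not establish that. The 17-point match and the 48 h spacing point to Days 8 and 10. The alternative slip of Day × 24 fits worse, since it would make 144 h Day 6, already listed as 120 h. But this is inference: the two columns could equally stay empty while Days 8 and 10 are added correctly. What stands is that neither reading leaves the list right, because 7.2.1 has no other entry for Days 8 or 10.

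**The shell note is open-ended.** It reads "48, 96, 120, 144, and 192 hours postdose (additional time points might be added depending on the conduct of the study". Day 12 PK could be admitted this way, so it is too strong to say the PK tables will lack that column. The note does not correct 144 h or 192 h.

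**Other displays would expose an error.** The aPTT value tables carry a Day label above the sampling time, and Appendices 16.2.5.4 and 16.2.5.5 list actual draw times. This helps, but the Day label is specified only for Tables 14.2.5.1.1 to 14.2.5.1.3, not for the change-from-baseline tables or the mean figures.

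**The consequence is modest.** A reader might also infer that a return-to-baseline endpoint is misdated. No such endpoint is defined; the outputs are descriptive. The dose rationale expects activity of perhaps a day at 0.25 mg/kg and cites an aPTT effect of at least 72 h at 0.5 mg/kg, so much of the decline may fall by 120 h, where the labels are right. PK parameters use actual times, and late PK may be below quantitation. All of this stands and limits the point to displays.

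**The protocol prints no hour for Days 8, 10 or 12.** It puts the final visit about 12 days after the dose, which would be 288 h, while its own scale gives 264 h. This also stands; neither figure is in the SAP list.

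**Conclusion.** The mismatch is certain: 144 h and 192 h fall on days with no protocol visit, one 17-point list serves two schedules that the protocol counts as 16 and 17, and SAP section 9 declares no change.

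The consequence is conditional. Day 8 and Day 10 aPTT either could be labelled about 24 h early or have no listed nominal time. Two PK times correspond to no planned sample, and Day 12 PK has no listed time unless one is added under the shell note.

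The effect is limited to by-time summaries and mean plots for secondary and other outcomes. It does not touch the primary safety objective and has little effect on AUC, Kel, half-life, CL or Vss. The conclusion rests on the (Day - 1) × 24 scale, which matches every hour the protocol prints for Days 2 to 6, and on the footnotes and Table 4 counts agreeing about the late samples. It should be corrected before the tables are programmed.

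**What to change.** Replace the shared list in SAP 6.1, 7.2.1 and the Section 11.3 shell note with two lists that follow the flow chart and Table 4:
- **PK (16 points):** the existing times from predose to 120 h, plus Day 12, nominally 264 h. Add a note that the protocol also describes this visit as about 12 days after dosing, and settle one label.
- **aPTT (17 points):** the existing times from predose to 120 h, plus Day 8 and Day 10 before dialysis, nominally 168 h and 216 h. Keep the Day 12 pre- and post-dialysis values already in 7.2.1.

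Showing study day beside the hour for all late samples, including in the change-from-baseline tables and mean figures, would remove any doubt, since the protocol defines those visits by day.

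If samples on Days 7 and 9 were intended, say so in SAP section 9 and reconcile the protocol flow chart and Table 4 with it.

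Aligning the SAP with the protocol changes only its wording and shell columns: no new samples and no change to PK parameter methods. The Days 7 and 9 alternative would also need a change to the protocol schedule.

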### **6.2 Bioanalytical Method**

Plasma concentrations of xisomab 3G3 will be determined using enzyme-linked immunosorbent assay (ELISA) validated with respect to accuracy, precision,

linearity, sensitivity, and specificity at Celerion, Lincoln, Nebraska. The analytical range (lower limit of quantitation [LLOQ] – upper limit of quantitation [ULOQ]) for xisomab 3G3 is expected to be 50 – 5000 ng/mL.

### **6.3 Investigational Product and PK Analyte Information**

#### **6.3.1 Xisomab 3G3**

Xisomab 3G3 is a novel, injectable, therapeutic monoclonal antibody (IgG4, S241P hinge-modified) that prevents activation of the contact (intrinsic) pathway of coagulation and is intended to address the problem of dose limiting bleeding side effects of current antithrombotic agents. Xisomab 3G3 was developed by Aronora, Inc. and is intended for IV administration. The proposed indication for xisomab 3G3 is as a therapeutic treatment of venous thromboembolism. The goal of xisomab 3G3 treatment is to achieve safe anticoagulation for several days with a single dose.

Xisomab 3G3 and matching placebo was supplied as sterile powder for injection via the IV route, upon reconstitution.

The quantity referenced for doses are based on active drug substance (i.e., xisomab 3G3); therefore, dose adjustment is not required for calculation of dose-dependent PK parameters for the parent drug.

